### **9.1.1. Adverse Events Leading to Withdrawal**

AEs leading to withdrawal of study drug will be flagged in the AE listing, displaying details of the event(s) captured on the CRF.

### **9.1.2. Deaths and Serious Adverse Events**

No deaths occurred during the course of study.

## **9.2. Local Tolerability Assessments**

The investigator's assessment of the application site reaction will be summarized by study visit and treatment group using both categorical methods (number and percentage of subject with each score) as well as continuous methods (e.g., mean, median, etc.). Categorical summaries will be provided for dermal response as well as other effects. No inferential statistical tests will be performed. This assessment should be performed prior to the application of IP in the study site. Subjects not meeting this condition on baseline visit are completely removed from the table summary.

The subject's assessment of the application site reaction will be summarized similarly. This assessment should be performed 10 – 15 minutes after the application of IP in the study site. Subjects not meeting this condition on baseline visit are completely removed from the table summary.

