**Table 1: Schedule of Events**

Study Procedure	Screen	Baseline Day 1	Wk 4 Day 29	Wk 8 Day 57	Wk 12 Day 85	Wk 16 Day 113	Wk 20 Day 141	Wk 24 Day 169	Wk 25 Day 176
Visit	1	2	3	4	5	6	7	8	9
Visit Window	-35 days		+/- 5 days	+/- 5 days	+/- 5 days	+/- 5 days	+/- 5 days	+/- 7 days	+/- 7 days
Informed consent	X								
Demographics	X								
Fitzpatrick skin type assessment	X								
Medical and surgical history	X								
Physical examination a	X	X			X				X
Vital signs, height, weight b	X	X	X	X	X	X	X	X	X
I/E criteria	X	X							
Randomization		X							
Hematology, Serum Chemistries, UA, TSH/T4	X	X	X		X			X	
Lipid (Fasting) c		X						X	
Resting 12-lead ECG	X		X		X			X	
BSA d (Full Body), T-VASI e	X	X			X			X	
F-BSA d , F/N-BSA d , BSA (Hands, Forearms, Elbows) d , F-VASI e , F/N-VASI e , FOREARM-VASI e , HAND-VASI e , FsIGA f	X	X	X	X	X	X	X	X	X
VNS g , PaGIC-V h			X	X	X	X	X	X	
VitiQoL i		X	X	X	X	X	X	X	
Local Tolerability Assessments j		X	X	X	X	X	X	X	
Digital Photography k		X	X	X	X	X	X	X	
Urine pregnancy test l		X	X	X	X	X	X	X	X
Serum pregnancy test m	X								

AD-ST-33.06 Effective date: 12-Nov-2020

Study Procedure	Screen	Baseline Day 1	Wk 4 Day 29	Wk 8 Day 57	Wk 12 Day 85	Wk 16 Day 113	Wk 20 Day 141	Wk 24 Day 169	Wk 25 Day 176
Visit	1	2	3	4	5	6	7	8	9
Visit Window	-35 days		+/- 5 days	+/- 5 days	+/- 5 days	+/- 5 days	+/- 5 days	+/- 7 days	+/- 7 days
Follicle-StimulatingHormone (FSH) a	X								
PK Sampling b		X	X		X			X	
NB-UVB Phototherapy inclinic c		X							
Return of USB stick to sitefor phototherapy data uploading d			X	X	X	X	X	X	
Dispense IP kit e		X	X	X	X	X	X		
IP application in clinic f		X	X	X	X	X	X		
Dispense/review diary		X	X	X	X	X	X		
Weigh IP tubes g		X	X	X	X	X	X	X	
Compliance calculation h			X	X	X	X	X	X	
Adverse event assessment i	X	X	X	X	X	X	X	X	X
Concomitant medications	X	X	X	X	X	X	X	X	X

a Limited physical examination: skin, lungs, and heart only

b Height will be measured at Baseline only. Weight will be collected at screening, baseline and Week 24.

c Fasting required for a minimum of 8 hours prior to blood draw

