- h The Patient Global Impression of Change-Vitiligo (PaGIC-V) is a 7-point scale on which the subject will rate improvement compared to baseline and will be evaluated for the face only.
- i The Vitiligo Quality of Life (VitiQoL) is a 16-item questionnaire with a 7-point numerical scale from (0 - Not at all) to (6 - All of the time). The VitiQoL is completed by the subject.
- j Tolerability assessments should be recorded prior to study drug application for Investigator assessment and 10-15 minutes post-drug application for subject ('0-3' burning/stinging assessment). Investigators will specify if any application site reaction is due, in whole or in part, to the effects of phototherapy treatment. Only the Investigator assessment will take place on Week 24.
- k Digital Photography will be conducted at all sites for all subjects. Required study photos will be taken of the treatment areas during the Baseline Visit. In addition, a photo of the facial target patch will be taken as reference for the VNS assessment. Fixed, multi-angle photos will be taken at select sites for additional evaluation.
- l A urine pregnancy test will be administered to all females of child-bearing potential. A negative result is required for continued participation in the study, and results must be available prior to dispensing of study drug at each visit.
- m Serum pregnancy testing will be performed at Screening; a negative result is required for participation in the study.
- n FSH will be performed (if indicated) at Screening to confirm post-menopausal status.
- o PK samples will be collected from all subjects at Baseline, Week 4, Week 12, and Week 24. The samples will be drawn prior to application of the investigation product in the clinic. Subjects should apply investigational product 11-12 hours before the PK collection time.
- p NB-UVB Phototherapy treatment will occur in the clinic at the Baseline Visit prior to the initial IP application. The treatment will be per the NB-UVB Treatment Protocol and be tailored per the subject's Fitzpatrick Score. The subject will be provided with the phototherapy unit in addition to a USB stick which will be inserted into the unit to obtain phototherapy data during the course of the treatment period.

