- q Subjects should be instructed to return the USB stick from the phototherapy unit to site for the uploading of the phototherapy data. Once the data has been uploaded by the site staff, a new USB stick should be provided to the subject to insert into the NB-UVB phototherapy unit.
- r IP kits will be dispensed based on % BSA affected. See IP Handling Manual for details.
- s Subjects to apply assigned IP in clinic at these visits. The time of application will be documented.
- t Each IP tube will be weighed prior to dispensing at the Baseline visit and at each follow-up clinic visit according to the Schedule of Visits and Assessments. When IP is applied in the clinic, the IP tube will be weighed before and after IP application. See IP Handling Manual for details.
- u Compliance calculation is described in the IP Handling Manual.
- v Adverse Events (AEs) and clinically significant abnormal laboratory test value(s) will be evaluated by the PI and treated and/or followed up for up to 30 days after end of treatment or until the symptoms or value(s) return to normal, or acceptable levels, as judged by the PI.

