## **9.3. Clinical Laboratory Evaluations**

Laboratory test results will be summarized descriptively by treatment and study visit as both observed values, changes, and percent changes from baseline values for continuous hematology, chemistry, and urinalysis results. Categorical urinalysis results will be summarized using frequencies by study visit and treatment.

Abnormal results will be flagged in the listings.

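### SAP 9.2 drops a subject from the whole by-visit tolerability table for one mistimed baseline rating, while ratings mistimed at later visits stay in

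*SAP*

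**What the plan says.** SAP 9.2 has one paragraph for each tolerability rating. The investigator's rating "will be summarized by study visit and treatment group using both categorical methods", with mean and median scores added. For the subject's rating, the "assessment of the application site reaction will be summarized similarly". Each paragraph states when its rating should be taken: before the in-clinic application for the investigator, 10 to 15 minutes after it for the subject. Each then closes with the same sentence: "Subjects not meeting this condition on baseline visit are completely removed from the table summary".

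The timing condition comes from footnote j of SAP Table 1, which names no particular visit: "Tolerability assessments should be recorded prior to study drug application for Investigator assessment and 10-15 minutes post-drug application for subject". It adds: "Only the Investigator assessment will take place on Week 24". The row "IP application in clinic" is marked at Baseline and Weeks 4, 8, 12, 16 and 20, and footnote s says: "Subjects to apply assigned IP in clinic at these visits. The time of application will be documented".

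Other sections that bear on the point:

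- SAP 9 runs all safety analyses on the Safety population.
- SAP 4.1 bases by-visit denominators on subjects with non-missing data at the visit.
- SAP 6.1.5 applies no windowing and uses the nominal visit.
- SAP 6.1.1 defines the subject-rating baseline as the last non-missing value on the day of first application, without the 10 to 15 minute condition.
- Protocol 6.3.2 plans by-visit counts, percentages and mean/median scores, with no timing exclusion.
- SAP 10, which lists departures from the protocol analyses, does not mention this one.

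**The concern.** The exclusion is too broad in one direction and too narrow in the other. It acts on the subject when the fault lies in a single rating, so correctly timed on-treatment scores leave the table with the faulty one. It also looks at baseline only, although the same condition applies wherever cream is applied in clinic.

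Local tolerability is a listed safety endpoint (SAP 2.2.2). After termination, the efficacy output is cut to F-VASI summaries, so the safety tables are most of what the study will report. Adverse event tables do not fully replace the graded scores: under Protocol 5.7.1, an irradiated-site reaction counts as an adverse event only if it exceeds what the Investigator expects, needs medical intervention or leads to stopping phototherapy. Milder reactions may show only in the dermal response (0 to 7), other-effects or burning/stinging (0 to 3) scores, and these are what a removed subject loses from the table.

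SAP 9.6 also removes subjects from a table, but attributes that to a sponsor request. SAP 9.2 gives no basis for removing the subject rather than the rating.

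**Working it through.** The plan gives no figure to reproduce. The check is a reading of the text and a count from the schedule.

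**1. Does a later visit need a valid baseline?** SAP 9.3 plans laboratory summaries as "both observed values, changes, and percent changes from baseline values". SAP 9.2 plans frequencies and score summaries at each visit and no change from baseline. A Week 8 score can therefore be tabulated whether or not the baseline rating was on time. The subject's baseline rating is itself taken after the first application, so it is not a pre-treatment reference in any case.

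**2. Ratings on the schedule (SAP Table 1).**

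- Investigator, post-baseline: Weeks 4, 8, 12, 16, 20, 24 = 6.
- Subject, post-baseline: Weeks 4, 8, 12, 16, 20 = 5 (Week 24 is investigator only).

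**3. Ratings lost per removed subject.** If the last scheduled visit attended was Week k, at most k/4 correctly timed later ratings are dropped from the table concerned:

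| Last scheduled visit (k) | 0 | 4 | 8 | 12 | 16 | 20 |
|---|---|---|---|---|---|---|
| Later ratings dropped (k/4) | 0 | 1 | 2 | 3 | 4 | 5 |

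One more investigator rating is lost if the Week 24 or early termination rating is tabulated. Protocol 5.5 gives the early termination visit the Week 24 procedures, so no subject rating is added there. Ceiling: 5 + 1 = 6 investigator ratings, or 5 subject ratings, dropped to exclude 1 mistimed rating. SAP 3 says no subject completed treatment, so actual losses will be smaller.

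**4. Visits screened.** Cream is applied in clinic at 6 visits. SAP 9.2 screens 1 and leaves 5 of 6 (5/6 = 83%) unscreened. Nothing in SAP 4.1, 6.1.5 or 9.2 removes a mistimed rating at those five.

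**5. Two subjects compared.**

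| | Baseline rating | Weeks 4 to 20 | Ratings from Weeks 4 to 20 in the table |
|---|---|---|---|
| Subject A | mistimed | all on time | 0 of 5 |
| Subject B | on time | all mistimed | 5 of 5 |

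**6. Illustration only.** The documents give no mistiming rate. Assume a rate q at each visit, independent between visits. Per 100 subjects with a rating at a given later visit, 100 × q × (1 − q) correctly timed ratings are lost and the same number of mistimed ones are kept: 1.96 at q = 2%, 4.75 at 5%, 9 at 10% and 16 at 20%. The two counts are equal because of the independence assumption. A rule applied to the rating brings both to 0.

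**The case against.** The strongest reply is that this is tidying of two descriptive tables in a terminated study. No test or decision uses them, adverse events stay on the full Safety population, no imbalance between arms is shown, and nobody may be affected. All of that stands, and it keeps the point at low severity.

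Second, restricting the table to subjects with a valid baseline gives the same cohort at each visit, and SAP 6.1.1 does define a baseline for the subject rating. A baseline screen also has some logic for the investigator rating, since a score taken after the first application is no longer pre-treatment. This explains leaving out the baseline value. It does not explain discarding later on-time scores from a table with no change from baseline, and it does not reach the subject rating, which is post-application at every visit.

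Third, SAP 9.2 does not say in words that later mistimed ratings stay in. That is an inference, and SAP 6.1.5 concerns visit windows rather than minutes around an application. But the condition is written for baseline alone and no other text removes such ratings, so the inference is the natural reading.

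Fourth, footnote s records the time of application, not of the rating. If rating times were not captured after baseline, the uneven screening reflects a data limit. That is a fair caveat for the fix; it still does not justify dropping later ratings.

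Fifth, SAP 9.2 removes subjects from the table, not from the study record. The text does not settle this: SAP 6.1.8 keeps data not analysed under the plan out of listings and datasets as well. The loss claimed here is from the table only.

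The silence of Protocol 6.3.2 carries little weight, since Protocol 6.1 leaves detail to the SAP.

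**Conclusion.** The concern holds. SAP 9.2 applies a subject-level exclusion, triggered at one visit, to by-visit tables that have no analytic need for it, and leaves the same timing fault untouched at the other five in-clinic application visits. It is an explicit exception to the Safety-population default, not a hidden contradiction. It is stated without a reason.

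The ceiling is 6 investigator or 5 subject ratings lost per removed subject. The number of subjects affected and the achieved arm sizes are not given, so no total and no share of an arm can be stated. No effect on any inference is claimed. Two readings support the conclusion: that each paragraph's condition removes the subject only from its own table, and that later mistimed ratings are kept because nothing excludes them. It should be fixed because the correction is cheap, but it sits at the low end of importance.

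**What to change.** In both paragraphs of SAP 9.2, replace removal of the subject with one rule on the rating, applied alike at every in-clinic application visit. For example: *a rating not taken in the required time relation to the in-clinic application is excluded from (or shown flagged in) the summary for that visit only; all Safety-population subjects and all their other ratings are kept.* Add a table footnote with the number of mistimed ratings by arm and visit, and align SAP 6.1.1 with the rule. Week 24 has no in-clinic application, so its investigator rating needs no timing screen.

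This assumes that rating times were recorded at later visits, as they must have been at baseline for the present rule to work. If they were not, say so in the footnote and keep the post-baseline ratings anyway.

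Cost: two sentences in 9.2, one line in 6.1.1 and a timing flag in programming. The price is a footnote and slightly smaller, or flagged, counts at the visits concerned.

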## **9.3. Clinical Laboratory Evaluations**

Laboratory test results will be summarized descriptively by treatment and study visit as both observed values, changes, and percent changes from baseline values for continuous hematology, chemistry, and urinalysis results. Categorical urinalysis results will be summarized using frequencies by study visit and treatment.

Abnormal results will be flagged in the listings.

## **9.4. Vital Signs**

Descriptive summaries of observed values, changes, and percent changes from baseline will be calculated for systolic blood pressure, diastolic blood pressure, heart rate, weight, BMI, and oral body temperature by treatment group and study visit.

## **9.5. 12-Lead Electrocardiograms**

Descriptive summaries for observed values and change from baseline will be presented for 12-lead ECG measures of PR interval, QRS interval, QT interval, QTc interval (Fridericia's [QTcF] correction method), and heart rate. These summaries will be presented by study visit and treatment group.

The number and percentage of subjects with each ECG investigator interpretation (normal; abnormal, not clinically significant; or abnormal, clinically significant) will be displayed for each treatment group and study visit. If the interpretation results are different in CRF and external data, only the CRF data will be summarized in the tables. If the interpretation results are just collected in one source, that will be used for table summaries.

## **9.6. Physical Examination**

The number and percentage of subjects with normal; abnormal, not clinically significant; or abnormal, clinically significant findings in the physical examination will be displayed at each study visit by body system and treatment group. Subjects having abnormal findings with description of Vitiligo are removed from table summary upon the sponsor request.

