### 1.3. Schedule of Visits and Assessments

Study Procedure	Screen	Baseline Day 1	Wk 4 Day 29	Wk 8 Day 57	Wk 12 Day 85	Wk 16 Day 113	Wk 20 Day 141	Wk 24 Day 169	Wk 25 Day 176
Visit	1	2	3	4	5	6	7	8	9
Visit Window	-35 days		+/- 5 days	+/- 5 days	+/- 5 days	+/- 5 days	+/- 5 days	+/- 7 days	+/- 7 days
Informed consent	X								
Demographics	X								
Fitzpatrick skin type assessment	X								
Medical and surgical history	X								
Physical examination a	X	X			X				X
Vital signs, height, weight b	X	X	X	X	X	X	X	X	X
I/E criteria	X	X							
Randomization		X							
Hematology, Serum Chemistries, UA, TSH/T4	X	X	X		X			X	
Lipid (Fasting) c		X						X	
Resting 12-lead ECG	X		X		X			X	
BSA d (Full Body), T-VASI e	X	X			X			X	
F-BSA d , F/N-BSA d , BSA (Hands, Forearms, Elbows) d , F-VASI e , F/N-VASI e , FOREARM-VASI e , HAND-VASI e , FsIGA f	X	X	X	X	X	X	X	X	X
VNS g , PaGIC-V h			X	X	X	X	X	X	
VitiQoL i		X	X	X	X	X	X	X	
Local Tolerability Assessments j		X	X	X	X	X	X	X	
Digital Photography k		X	X	X	X	X	X	X	
Urine pregnancy test l		X	X	X	X	X	X	X	X
Serum pregnancy test m	X								
Follicle-Stimulating Hormone (FSH) n	X								

Study Procedure	Screen	Baseline Day 1	Wk 4 Day 29	Wk 8 Day 57	Wk 12 Day 85	Wk 16 Day 113	Wk 20 Day 141	Wk 24 Day 169	Wk 25 Day 176
PK Sampling o		X	X		X			X	
NB-UVB Phototherapy in clinic p		X							
Return of USB stick to site for phototherapy data uploading q			X	X	X	X	X	X	
Dispense IP kit r		X	X	X	X	X	X		
IP application in clinics s		X	X	X	X	X	X		
Dispense/review diary		X	X	X	X	X	X		
Weigh IP tubes t		X	X	X	X	X	X	X	
Compliance calculation u			X	X	X	X	X	X	
Adverse event assessment v	X	X	X	X	X	X	X	X	X
Concomitant medications	X	X	X	X	X	X	X	X	X

a Limited physical examination: skin, lungs, and heart only

b Height will be measured at Baseline only. Weight will be collected at screening, baseline and Week 24.

c Fasting required for a minimum of 8 hours prior to blood draw

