###### **Main Criteria for Inclusion:**

1. Subject is legally competent to sign and give informed consent.
2. Males and females ages 18-21 years with Fitzpatrick Skin Type IV-VI or age 22 years and older with Fitzpatrick Skin Type I-VI.
3. Clinical diagnosis of non-segmental vitiligo involving face.
4. A Facial Vitiligo Area Severity Index [F-VASI] score of  $\geq 0.25$  at baseline.

5. Vitiligo of the face involving at least  $\geq 0.25\%$  body surface area (BSA) involvement (ie, one quarter of one handprint). Subjects may have non-facial vitiligo elsewhere which will not be included in the minimum BSA. The maximum BSA (total body inclusive of the face, whether or not in areas to be treated in this study) permitted is 15%.
6. Subjects with vitiligo on the hands, forearms, or elbows agree to treat these areas in addition to the face, with investigational product and phototherapy.
7. Subject agrees to discontinue all agents used to treat vitiligo from screening through the final safety follow-up visit. Over-the-counter preparations deemed acceptable by the Investigator and camouflage makeups are permitted.
8. Female subject of childbearing potential (FOCBP) must have a negative serum pregnancy test at Screening and negative urine pregnancy test at Baseline (Visit 2). For FOCBP involved in any sexual intercourse that could lead to pregnancy: the subject must agree to use a highly effective contraceptive method for at least 4 weeks prior to Day 1. Additionally, from Day 1 until at least 4 weeks after the last investigational product administration, these subjects must agree to use at least 1 highly effective contraceptive method in addition to 1 barrier method. [Figure 1](#)
9. Female subject of non-childbearing potential must either be post-menopausal with spontaneous amenorrhea for at least 12 months prior to baseline (post-menopausal status will be confirmed with FSH testing) or have undergone surgical sterilization (permanent sterilization methods include hysterectomy, bilateral oophorectomy, or bilateral salpingectomy). [Figure 1](#)
10. Males, if engaging in sexual intercourse with a female who is pregnant or a female of child-bearing potential, must agree to use a condom every time during the study and every time subsequently until 4 weeks beyond the last dose of investigational product.
11. Males must agree not to donate sperm from the first dose of investigational product until 4 weeks after the last dose of investigational product.

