### 5.1.3. Physical Examination

Physical examinations will be performed according to the Schedule of Visits and Assessments (Section 1.3). The physical exam will be limited to skin, lungs and heart only.

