### **6.1.3. Subjects to Analyze**

Three analysis populations will be defined:

- The Safety population will include all subjects who are enrolled and received at least one confirmed dose of investigational product. This population will be used for all safety analyses and will be defined separately for each treatment arm.
- The Intent-to-Treat (ITT) will include all subjects randomized in the study. This population will be the primary analysis for the analysis of efficacy endpoints.

- The PK population will include all subjects who are randomized and receive at least one application of investigational product and have at least one analyzed PK sample.

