## **10. Changes from Planned Analysis**

This study was planned for 24 weeks to evaluate safety and efficacy ARQ-252 Cream 0.3% in Subjects with Non-Segmental Facial Vitiligo. However, upon the sponsor discretion the study

terminated and all the subjects that were currently enrolled are early terminated. Due to this decision, the following actions were taken which deviates from the planned analyses in the protocol:

- Emergency unblinding was done after following Premier Research SOPs.
- Only summary statistics are provided for F-VASI and other safety endpoints.
- No statistical testing is performed and none of secondary endpoints are summarized.
- The SAP and shells are developed to provide only summary statistics and frequency distributions.

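### SAP 9.6 removes subjects, not the vitiligo finding, from the physical-examination table, without saying which rows or visits are affected

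*SAP*

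**What the plan says.** SAP 9.6 plans a table with three result categories: normal; abnormal but not clinically significant; and abnormal and clinically significant. Counts and percentages of subjects "will be displayed at each study visit by body system and treatment group". The next sentence reads "Subjects having abnormal findings with description of Vitiligo are removed from table summary upon the sponsor request". It gives no reason beyond the sponsor's request, no extent and no remaining denominator.

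Four other provisions bear on it:

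- **Entry disease.** Protocol 4.5.1, inclusion criterion 3, requires: "Clinical diagnosis of non-segmental vitiligo involving face".
- **Content of the examination.** Protocol 5.1.3: "The physical exam will be limited to skin, lungs and heart only". The skin is therefore examined every time.
- **Population.** Protocol 6.1.3 says of the Safety population: "This population will be used for all safety analyses and will be defined separately for each treatment arm". SAP 9 repeats that all safety analyses use it and states no exception.
- **Denominator.** SAP 4.1 bases by-visit displays on subjects of the relevant population who have non-missing data at that visit.

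SAP 9.2 has a comparable removal rule for the tolerability tables, and there the extent is stated: "Subjects not meeting this condition on baseline visit are completely removed from the table summary".

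**The concern.** A safety table should describe the subjects who were examined. Here, staying in the table depends on a recording habit. Two subjects with the same facial vitiligo and the same clear lungs and heart are treated differently if one examiner records the known disease as an abnormal skin finding and the other does not. That has nothing to do with safety.

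The missing scope is a second problem. Two programmers could follow the sentence faithfully and produce different tables, and a reader of the output could not tell which rule had been applied. At stake are lung and heart results on the literal reading, and skin findings other than vitiligo on the narrower one.

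**Working it through.** The documents give no figure for this table, so there is nothing to reproduce. The check compares the text and makes a small count from the visit schedule.

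**1. What is removed.** The grammatical object of the sentence in SAP 9.6 is the subject. The trigger is an examination finding recorded as abnormal and described as vitiligo, not the diagnosis itself. Every subject has the diagnosis, so any subject can meet the trigger. Whether a subject does depends on what was written down.

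**2. Extent.** SAP 9.2 says removal is complete. SAP 9.6 uses similar wording without that qualifier. The table is laid out by visit and body system, so removal could apply to the whole subject, to all systems at one visit, to the skin row at all visits, or to the skin row at one visit.

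**3. Which results can exist after baseline.** Inputs:
- Body systems: 3 (Protocol 5.1.3).
- Scheduled examinations: Screening, Baseline, Week 12 and Week 25 (Protocol 1.3; SAP Table 1).
- All enrolled subjects were terminated early and none completed treatment (SAP 3).
- The early termination visit follows Week 24 procedures (Protocol 5.5), and the schedule has no physical examination at Week 24.

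Screening and Baseline results are pre-treatment. That leaves Week 12 as the post-baseline examination that can be counted on from the schedule: 1 examination × 3 systems = 3 results per subject, for subjects who reached it.

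**4. Loss among those 3 results, by reading.**

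| Reading of the sentence | Vitiligo recorded at Week 12 | Recorded only at Screening or Baseline |
|---|---|---|
| Subject leaves the whole table | 3 of 3 | 3 of 3 |
| All systems, that visit only | 3 of 3 | 0 of 3 |
| Skin row, all visits | 1 of 3 | 1 of 3 |
| Skin row, that visit only | 1 of 3 | 0 of 3 |
| Vitiligo recoded at record level | 0 of 3 | 0 of 3 |

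**5. Number of subjects.** If a share f of examined subjects meets the trigger, the affected rows keep a share 1 − f. The documents give neither f nor actual enrolment. As an assumed range, f = 50% leaves 50%, f = 90% leaves 10% and f = 100% leaves none. No value in that range is supported over another.

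**6. Against the SAP's own rules.** A removed subject is in the Safety population and has non-missing examination data, but is not counted. On the literal reading this departs from SAP 9 and SAP 4.1 in all three rows. On a skin-row reading it departs from them in the skin row only; the lung and heart rows keep every examined subject.

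**The case against.** The best defence is that the sentence echoes the counted unit of the table. SAP 9.6 has just spoken of subjects with findings by body system, so taking the vitiligo entry out of the affected cell is a natural reading and probably the intended one. This stands to the extent that loss of lung and heart data is not established. It does not remove the defect: the intent is not written, and even the narrow reading drops a subject's other skin findings.

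A second defence is that an openly stated exclusion for one table qualifies the general rules. The rule is indeed disclosed. But SAP 9 allows no exception, and SAP 9.6 supplies no replacement denominator.

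A third is that little depends on the table, and this largely stands. There is no hypothesis testing. Protocol 6.3.3 sends clinically significant examination changes to the adverse-event tabulations. Application-site reactions have their own tables (SAP 9.2), irradiation reactions beyond the expected become adverse events (Protocol 5.7.1), and vital signs and ECGs are summarised separately.

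Three stronger readings are tempting but not supported:

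- A reader might infer that SAP 10 wrongly omits this removal. That section concerns the termination decision, saying that "the following actions were taken which deviates from the planned analyses in the protocol". The protocol's examination section plans no such table, and nothing ties the removal to termination. It is not clearly an omission.
- A reader might count results over all four scheduled examinations. That needs a Week 25 examination, which the early-termination procedures do not provide, and it mixes in pre-treatment results.
- A reader might infer that the removed results also disappear from listings and datasets, because SAP 6.1.8 leaves out data not analysed. SAP 9.6 speaks only of the table summary, so the documents do not establish this.

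**Conclusion.** The point holds as a wording defect of low severity. As written, the rule takes subjects out of a safety table according to how known disease was recorded, and leaves rows and visits undefined. The effect is confined to one descriptive table and mainly to findings that are not clinically significant. At Week 12, between 0 and 3 of a removed subject's 3 results are lost, depending on the reading. How many subjects are affected cannot be estimated, and nothing in the documents suggests a direction of bias between arms.

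This assumes that examinations followed the schedule and that early-terminated subjects had the Week 24 procedures. Removal of every subject is possible on the text, but it is not shown.

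**What to change.** Replace the sentence in SAP 9.6 with a single rule that has three parts:

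1. Where vitiligo is the only abnormal skin finding, recode that record to its own skin category, for example *disease under study only*.
2. Keep every examined Safety-population subject in the denominator for skin, lungs and heart at each visit.
3. Where the skin result shows vitiligo plus another abnormality, classify it by the other abnormality.

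The separate category is needed. If the vitiligo finding were simply ignored while the subject stayed in the denominator, a vitiligo-only skin result would fall in no category and the percentages would not sum to 100. Recoding still keeps known disease out of the abnormal counts, which is presumably what the sponsor wanted.

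The cost is one SAP sentence, a record-level recode in programming, and a light review of free-text skin descriptions to separate vitiligo from other findings. If the tables have already been produced, the study report should state which reading was applied.
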